- 4) All patients may also be followed up as scientifically appropriate at least one year and up to five years regardless of initial findings in order to optimize correlation of imaging to clinical findings. It is not possible to do a template nodal dissection on all patients regardless of findings, and certainly not on nodal imaging negative patients. While it is true that we will not biopsy lymph nodes if all the imaging modalities are negative, there will be patients who are MR imaging positive but PET negative and visa-versa who will get biopsied. Yet biopsies or sampling will typically performed only when there is an identifiable target on anatomic imaging and will thus be standard of care. Some patients who undergo open or laparoscopic nodal sampling for positive findings will have a limited template dissection of adjacent imaging negative nodes (a standard practice). By clinical and ethical necessity, the imaging and biopsy negative patients will be confirmed by lack of lymph node progression on imaging as well as stable PSA levels. The standard of care outside the trial includes serial PSA measures as well as appropriate imaging such as CT or MR and repeat imaging as required.
- 5) A Ground Truth Panel composed of two urologists ([name] and [name] or substitute) and a radiation oncologist ([name] or substitute) will meet once sufficient data has been collected and/or communicated via email. The diagnostic imagers will not be included on this panel but will present the data. Truth will be ascertained via the criteria outlined below. If there were initial differences of opinion, further discussion will ensue until a group consensus can be achieved.

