6) Presence or absence of disease in the prostate bed will be confirmed by biopsy only overridden by clinical data. For example, a substantial reduction in PSA after prostatic bed salvage therapy without a subsequent substantial PSA rise in at least 6 months would not only establish presence of presumed prostatic bed disease but also absence of extraprostatic disease. Extraprostatic nodal involvement per patient will be typically confirmed by pathologic proof or under certain circumstances by response after focal therapy if scientifically justifiable. Skeletal involvement will be confirmed with either biopsy or typical appearance on MR [41] or other accepted confirmatory imaging such as typical appearance on bone scan or CT. Absence of extraprostatic disease will typically be confirmed by either a substantial reduction in PSA after prostatic bed therapy without a substantial rise in at least 6 months as above, and/or stable appearance on CT or MRI for greater than 1 year without evidence of nodal or bone involvement as medically and scientifically appropriate. Because some patients had definitive follow-up for the prostate bed but not extraprostatic disease, and visa-versa, the number of patients in each sub-analysis may differ.

7) Patients who are prostate bed positive and extraprostatic negative may get treated with local therapy (radiation, cryoablation, salvage surgery, etc.) as appropriate. Most of these patients will not initially get hormonal therapy and will be entered into the followup group. It is true that some patients with either high Gleason scores, impending or with cord compression and/or pathologic fracture, hydronephrosis, and/or rapid PSA doubling time of less than 3 months will require hormonal therapy, but this is not the majority of patients (approximately 15-20% worst case scenario). The majority of patients (80-85%) will have low to intermediate risk disease and PSA recurrence reflecting the prevalence of low and intermediate risk disease in the United States. Therefore these patients can be followed off hormonal therapy but with local therapy as needed.

C1.8 Correlation of FACBC and MR to and Clinical Outcome

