Receiver Operating Characteristic (ROC) analysis will be conducted to instigate the predictive power of FACBC PET and MR and determine if a variation in standard criteria or if combined criteria better maximizes sensitivity, specificity and accuracy of *each technique* using Chi-square test. The predictive accuracy of each technique will be determined using the positive predictive value (PPV) relative to the clinical and pathologic findings. The PPV of imaging will be assessed by calculating the probability of obtaining clinical and pathological outcomes that confirm the predicted positive findings based on the individual and combined scans. A similar negative predictive value (NPV) will also be calculated based upon a negative pathologic sampling as well as clinical/imaging follow-up at least 1 year or more. Formal hypothesis testing will be conducted to obtain inferences regarding differences between the predictive accuracies of these two approaches.

Each case will be evaluated as follows:

- 1) Results of biopsy as well as clinical follow-up will be correlated with prediction of local and distant neoplastic involvement by MR and *anti*-[¹⁸F]FACBC PET-CT.
- 2) Results of biopsy of lymph nodes or other extra-prostatic sites as well as clinical follow-up will be correlated with prediction of extraprostatic neoplasia by MR and *anti*-[¹⁸F]FACBC PET-CT.
- 3) Registered PET and MR will be correlated both qualitatively and quantitatively to pathologic and clinical results and in the discrimination of prostatic from extra-prostatic recurrence.
- 4) **Thus, truth for presence of disease will be established by biopsy/pathology and/or appropriate clinical followup. Truth for absence of disease will be established via pathologic sampling as well as standard clinical follow-up for at least 6 months and up to five years. We believe there will be enough patients with biopsy and clinically followed-up negative lymph nodes to calculate a true negativity rate.**

E2.0 Secondary Aims

Aim 2. and Sub-aim 2a.

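### Section E.1 gives two different follow-up minimums for a disease-negative case, and neither its periods nor its tissue wording match the Ground Truth Panel's criteria in C1.7 for extraprostatic absence

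*Combined protocol and SAP*

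**What the plan says.** Four places in the combined protocol and SAP bear on when a patient counts as free of disease.

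- **E.1 Aim 1, opening paragraph.** NPV is to be calculated "based upon a negative pathologic sampling as well as clinical/imaging follow-up at least 1 year or more".
- **E.1 Aim 1, item 4.** "Truth for absence of disease will be established via pathologic sampling as well as standard clinical follow-up for at least 6 months", with an upper end of five years. The item goes on to expect "enough patients with biopsy and clinically followed-up negative lymph nodes to calculate a true negativity rate".
- **C1.7 items 4 and 5.** "All patients may also be followed up as scientifically appropriate at least one year and up to five years". Tissue is limited: "we will not biopsy lymph nodes if all the imaging modalities are negative". Patients negative on imaging and biopsy are instead confirmed by no nodal progression and a stable PSA; that sentence gives no duration. For the panel, "Truth will be ascertained via the criteria outlined below", which leads to item 6.
- **C1.7 item 6.** For the bed: "Presence or absence of disease in the prostate bed will be confirmed by biopsy only overridden by clinical data". For extraprostatic sites, absence is typically accepted on a marked fall in PSA after prostate bed therapy "without a substantial rise in at least 6 months as above, and/or stable appearance on CT or MRI for greater than 1 year". Skeletal disease may be confirmed by biopsy, by typical MR appearance, or by other imaging such as bone scan or CT.

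**The concern.** Specificity is TN/(TN + FP) and NPV is TN/(TN + FN), so both use the true-negative cell. E.1 plans an ROC analysis aimed at sensitivity, specificity and accuracy, and also formal tests of differences in predictive accuracy. If the rule that fills the true-negative cell is stated in two ways, it is unclear which men enter which denominator.

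The timing is also loose. C1.0 says the grant runs for one year, longer follow-up is something patients may have, the panel meets when enough data are in, and C1.8 allows later re-review. Follow-up of 6 to 12 months at the time truth is fixed is therefore possible, and the plan does not say in advance how such a man is classified.

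The skeletal point is separate because it concerns presence of disease. If the study MR, or the CT of the study PET-CT, can establish skeletal disease alone, the test under evaluation helps to set the standard it is judged against.

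**Working it through.** **Step 1. Reproduce the plan's expected counts.** Inputs: the PSA-group table in the rationale for Aim 2 and Sub-aim 2a, PSA ≥ 4 column (n = 73): bed only 41, nodes only 1, both 25; sample size 25.

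- Bed disease: (41 + 25)/73 × 25 = 22.6; the plan says about 23.
- Nodal disease: (25 + 1)/73 × 25 = 8.9; the plan says about 9.

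Both agree.

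**Step 2. How many men depend on the absence rule.**

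- Node-negative: 25 − 8.9 = 16.1, about 16.
- Bed-negative: 25 − 22.6 = 2.4, about 2.

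The absence rule therefore matters mainly at the extraprostatic site.

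**Step 3. Compare the rules for extraprostatic absence.**

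| Source | Minimum period | Tissue |
|---|---|---|
| E.1, NPV | 1 year | negative sampling, joined to follow-up |
| E.1, item 4 | 6 months | sampling, joined to follow-up |
| C1.7 item 4, imaging- and biopsy-negative men | none in that sentence | no nodal biopsy if all imaging is negative |
| C1.7 item 6, PSA route | 6 months after bed therapy | not required |
| C1.7 item 6, imaging route | more than 1 year | not required |

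**Step 4. Run three types of patient through the rules.**

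- *A: maintained PSA response after bed therapy, 6 to 12 months of follow-up, no nodal tissue.* Negative under C1.7 item 6. Meets item 4 of E.1 on time. Fails the NPV sentence on time, and fails both E.1 sentences on tissue if sampling is mandatory.
- *B: negative nodal sampling, 6 to 12 months of follow-up, no bed therapy.* Negative under item 4 of E.1. Fails the NPV sentence on time. Meets neither of the usual routes in C1.7 item 6, since the imaging route needs more than 1 year.
- *C: CT or MRI stable for more than 1 year, no nodal tissue.* Negative under C1.7 item 6. Meets both E.1 sentences on time and neither on tissue if sampling is mandatory.

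Type B shows that the time conflict remains however the tissue wording is read. C1.7 item 6 does allow patient numbers to differ, but between the bed and extraprostatic sub-analyses, not between two measures at one site.

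**Step 5. The prostate bed.** C1.7 item 6 does use biopsy there, subject to clinical override, so the tissue mismatch with E.1 is weak and concerns about 2 men.

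**Step 6. Skeletal truth.** C1.7 item 6 accepts typical MR or CT appearance. C1.3 includes MR of the abdomen and pelvis, and C1.2 includes an abdomen-pelvis CT used for anatomic imaging. Neither is excluded as proof. By the MR route, a lesion that is not cancer but looks typical would be scored as an MR success. By the CT route the direction is open, because C1.4 item 3 scores PET-CT by persistent uptake: a CT-typical lesion without uptake would count against PET-CT. Exclusion criterion 7 in section D (characteristic bone scan findings) should keep such cases few. The documents give no rate.

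**The case against.** The strongest reply is that one panel applies one set of criteria, those in C1.7 item 6, and that E.1 only summarises them. On that reading, item 4's range of 6 months to five years spans the routes, and the 1 year in the NPV sentence echoes the imaging route. This is a plausible account of where the figures come from. But E.1 ties neither minimum to a route and does not say that C1.7 prevails. A man accepted by the 6-month PSA route still fails the NPV sentence as written.

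Three stronger readings are tempting, and the documents do not support them.

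- *That the plan deliberately uses 6 months for specificity and 1 year for NPV.* Item 4 is a general rule for absence of disease and is not assigned to specificity. Two sets of negatives are possible under the wording but are planned nowhere.
- *That men negative on all nodal imaging can never be nodal true negatives.* C1.7 item 4 says how they are confirmed, without tissue. C1.7 item 2 also uses the same joining phrase loosely, in a list of sampling methods. The tissue point is therefore only that E.1 fails to match C1.7, and only for extraprostatic sites.
- *That the skeletal rule is shown to bias results, or that its CT route favours PET-CT.* It is a risk only, and the direction for CT depends on uptake.

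It is also fair to say that Aim 1 is preliminary, that the only power statement concerns mRNA, and that C1.7 item 4 contemplates at least one year of follow-up for everyone. If that happens, the time conflict affects nobody.

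**Conclusion.** The inconsistency is real and minor. E.1 states two minimums for a disease-negative case and matches neither the route-specific periods nor the no-tissue routes of C1.7. It bears on the extraprostatic site, where about 16 of 25 men would take their truth from the absence rule.

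That figure assumes that the PSA ≥ 4 rates apply to the whole sample, that nodal disease stands in for extraprostatic disease, and that the 73 − 67 = 6 men with no positive site were node-negative. The trial also admits men with PSA 2.0–3.99 and a short doubling time, in whom the protocol expects more extraprostatic disease than at longer doubling times, so 16 is approximate. The number of men who would be classified differently cannot be derived from the documents and may be zero; no effect on any accuracy estimate is claimed.

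The skeletal route is a small additional risk of incorporation bias, unquantified and probably confined to few cases.

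**What to change.** Reconcile E.1 with C1.7 items 4 to 6 into one absence rule, set out by site and by route. For each route, state the minimum follow-up and whether tissue is required, and say that this rule governs both E.1 and the panel. Use the same set of negatives for specificity and NPV at each site. Add a sensitivity analysis restricted to negatives with at least 1 year of follow-up.

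For skeletal disease, either state that the study MR, or the CT of the study PET-CT, does not establish truth on its own, or report extraprostatic accuracy with and without cases whose truth rests on index imaging.

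The cost is wording and small extra analyses, with no new procedure. The downsides are that the 1-year set may be small and imprecise, and that some cases may become indeterminate or be settled later.

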As has been outlined in the Preliminary Results section of this proposal, *anti*-[¹⁸F]FACBC has been demonstrated to 1) have high sensitivity in the detection of recurrent prostate carcinoma though with suboptimal specificity in the prostate bed, and 2) the ability to differentiate prostatic from extraprostatic recurrence with high accuracy. *anti*-[¹⁸F]FACBC may thus have specific advantages for imaging recurrent prostate neoplasia within a clinical setting over conventional imaging. Yet, MR, especially with the addition of diffusion weighted imaging, has been reported in preliminary studies to provide high accuracy especially in the characterization of prostate bed recurrence. We hypothesize that utilization of a transmolecular approach combining synthetic amino acid radiotracer PET imaging with multiparametric MR has the potential to identify the presence and location of recurrent prostate carcinoma to a higher accuracy than either modality alone. **Therefore the most comprehensive manner to assess our hypothesis that PET-CT imaging with *anti*-[¹⁸F]FACBC in combination with multiparametric MR will lead to improved patient care resulting from detection of local and distant recurrent disease (Specific Aim #1) is to undertake a prospective clinical trial designed to address these issues.**

Secondary Aims

Aim 2. To determine mRNA differences between prostate carcinoma recurrent in the prostate bed and extraprostatic locations and to correlate any difference with quantifiable imaging biomarker data such as SUV for *anti*-[¹⁸F]FACBC PET-CT and ADC for MR.

Within the structure of the clinical trial (the same 25 patients) we will obtain sufficient tissue to perform mRNA sequencing on samples to exploit differences between the genetic profiles of recurrent prostate carcinoma in the prostate bed versus metastases. Since approximately 30% of patients with PSA > 4 ng/ml by our experience manifest with both prostate bed and nodal recurrence, we believe at least 8-10 patients in whom this comparison can be directly made will be available for analysis. This may also occur with lower PSA levels with faster DT. We will then correlate any differences in genotypic profile with imaging biomarkers from synthetic amino acid PET and MR, such as SUV and ADC.

Sub-aim 2a. To evaluate protein expression of previously identified amino acid transporters (AATs) that have been implicated in the uptake of *anti*-[¹⁸F]FACBC.

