Also within the context of the clinical trial of 25 patients, we will, whenever there is sufficient tissue, determine if candidate amino acid transport (AAT) proteins identified from data obtained in an earlier study (Project 1: P-50 ICMIC) are expressed. We will perform IHC analysis of up to 7 candidate AAT or co-transporters, specifically PAT 1, LAT1, LAT2, 4F2hc, and ASCT2, LAT3 and ASCT1 to understand if the AAT whose mRNAs are increased in malignant prostate carcinoma and correlated with *anti*-[¹⁸F]FACBC uptake are expressed at the protein level by IHC analysis.

Rationale for Aim 2 and Sub-aim 2a.

As has been outlined in the Preliminary Results section of this proposal, there is preliminary data in the literature of gene expression and mutational differences between primary prostate carcinoma cells and those prostate metastases [7-9] as well as between bone metastases and non-osseous metastases [8]. We propose within the context of this clinical trial to provide tissue to further understand these differences both in the ability of prostate carcinoma to transport and retain amino acids measured as uptake of *anti*-[¹⁸F]FACBC and expression characteristic as studied by multiparametric MR such as ADC parameters on DWMR and uptake and retention of Gadolinium. If we can determine that there are gene expression differences between malignancy confined to the prostate bed and those that are extraprostatic, we can correlate these differences to PET uptake and MR appearance. Furthermore, we may also be able to derive incidental genotypic information that could be exploited on subsequent unrelated experiments. In addition, we have preliminary evidence based on our earlier research that PAT1, LAT2 and ASCT2 as well as LAT1, xCT, LAT3 and ASCT1 were associated with malignancy. Out of the AATs that were associated with malignancy, PAT1 expression had the strongest correlation coefficient relative to *anti*-3-[¹⁸F]FACBC uptake [38]. We believe that a study such as this one provides an ideal opportunity to obtain both prostatic and extraprostatic tissue from the same patient in order to test these hypotheses using the patient as his own control.

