Our rationale for utilizing patients with PSA ≥ 4 is as follows. A total of 127 patients have been studied already in an R-01 study of the diagnostic performance of *anti*-3-[¹⁸F]FACBC versus conventional imaging. If the patients are stratified by PSA level as in the table below, 41/73 were positive in the prostate bed only, 25 in both prostate bed and lymph nodes, and 1 in lymph nodes only. Thus, in the 25 patients whom will be studied in this population,

approximately 23 will be expected to have disease in the prostate bed and approximately 9 will have disease in nodes, most of the latter will also have disease in the prostate bed. This should provide sufficient tissue for the above secondary aims. In addition, we have demonstrated that greater extraprostatic involvement will occur with shorter DT even at lower PSA levels. Thus the addition of PSA 2.0-3.99 ng/ml plus DT \leq 10 months is a reasonable method to increase recruitment while still acquiring tissue from extraprostatic involvement.

PSA group	<4 (n=54)	\geq 4 (n=73)	Total(n=127)
Prostate bed only (+)	27	41	68
LN only (+)	3	1	4
Both	8	25	33
Total	38	67	105

We hypothesize that by identification of disease recurrence in the prostate bed and extra-prostatic locations, we can exploit differences in mRNA analysis to correlate these differences to synthetic amino acid transport as well as MR parameters such as ADC mapping, and also better understand the relationship of AAT protein expression to *anti*-3- ^{18}F FACBC uptake. **Therefore the most comprehensive manner to obtain tissue to test our hypotheses is within the context of this prospective clinical trial.**

[figure not shown]
C1.0 Research Design and Methods (Aim 1)

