Upon completion of the study and/or after additional follow-up, each patient may be re-reviewed by the same Ground Truth Panel to determine if the predicted findings on *anti*-[¹⁸F]FACBC scan and MR individually and in tandem match those of clinical and pathologic findings especially in regard to the identification of prostatic versus extraprostatic recurrence. Also at that time uptake parameters will be reviewed. At no time this study will interfere with proper therapy as determined by the patient's physicians and the patient.

C2.0 Study Design and Methods (Aim2 and Sub Aim 2a)

Rationale. We hypothesize that *anti*-[¹⁸F]FACBC uptake is mediated by a LAT protein subtype or subtypes. However, the precise LAT subtype involved in all cases is unknown. We also further hypothesize that there are genotypic differences between recurrent prostate carcinoma cells confined to the prostate bed and those that are extraprostatic and that these differences can be explored via proper identification of candidate tissue via transmolecular imaging to be performed at termination of study or when sufficient tissue has been collected.

Experimental Design. To test the above hypothesis, we will compare mRNA expression of recurrent prostate carcinoma tissue within the prostate bed and extraprostatic. In addition we will utilize *anti*-[¹⁸F]FACBC avid tissue to confirm that the following AAT subtypes based on preliminary data are expressed at the protein level: PAT 1, LAT1, LAT2, 4F2hc, and ASCT2, LAT3 and ASCT1. We will study 8-10 samples of each recurrent prostate carcinoma in the prostate bed and 8-10 samples of disease outside the prostate bed, preferably in the same patient. We predict that one or more AAT subtypes will be relatively overexpressed by IHC in FACBC-avid carcinoma. We also predict that there will be differences in mRNA expression

based on these tissue samples between disease confined to the prostate bed and those that are extraprostatic. Based upon tissue availability we will perform IHC in the following rank priority: First: PAT 1; Second: LAT1, LAT2, 4F2hc; Third: ASCT2, LAT3 and ASCT1. This priority ranking is based on our desire to first confirm phenotypic expression of PAT1, since presence of this AAT correlated most strongly with *anti*-[¹⁸F]FACBC uptake, followed by LAT1 and LAT2 with the heterodimeric associated protein 4F2hc, and ASCT2, LAT3 and ASCT1.

C 2.1 Quantitative next-generation mRNA sequencing

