Methods. For experiments on fixed tissue RNA will be extracted at the Cancer Genomics Shared Resource (CGSR) at the Winship Cancer Institute from macrodissected 5 micron sections. The CGSR has extensive experience in preparing Total RNA from FFPE tissues [42]. FFPE RNA extraction will be performed using the Omega Biotech methodology in 96-well format on a Kingfisher FLEX Liquid Handler Robot. FFPE RNA will be quantitated by nanodrop spectrophotometry, and tested for RNA integrity and quality by Taqman analysis of the RPL13a ribosomal protein. Samples with sufficient yield (>500 ng), A_{260}/A_{280} ratio > 1.8 and RPL13a C_T values less than 31 cycles will be used for preparing sequencing libraries using the TrueScript kit (Illumina). Amplified cDNA libraries will be sonicated to an average length of 250 bp with a Covaris E-120 Adaptive Focused Acoustics Instrument. We will repair the ends of the sonicated DNA using the Illumina TrueScript protocol and generate barcoded libraries for RNA-seq analysis on an Illumina HiSeq 2000 instrument at the Southern California Genotyping Consortium at UCLA. Agilent Bioanalyzer Nanochip analysis will be performed to ensure the integrity of libraries prior to sequencing. We will obtain 60 million reads per sample of 50bp paired-end sequencing reads using the Illumina version 3 kits with three samples multiplexed per sequencing lane.

Fluorogenic quantitative RT-PCR assays will be used to confirm changes identified by RNA-seq analysis and performed in triplicate with standard SYBR-Green methodology on the I-cycler system (Bio-Rad, Hercules, CA, USA) according to published protocols with minor modifications [43]. Reaction specificity will be assessed by melting point analyses, in which single melting point peaks are required at temperatures predicted by amplicon sequence. Reactions without reverse transcription and template will serve as controls for DNA contamination and specimen carry-over. Test gene expression will be normalized to 28S ribosomal RNA and referenced to a standard RNA specimen. Relative normalized gene expression of each LAT subtype will be compared in FACBC avid versus non-avid prostate carcinoma, with statistical significance assessed by analysis of variance (ANOVA).

C 2.2 Immunohistochemistry

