Methods. Fixed tissue sections (5 μ m thickness) will be dewaxed, and steam antigen retrieval will be performed at pH 6.5 in a pressure cooker for 20 minutes [44]. Tissue sections will be incubated with primary antibodies directed against PAT 1, LAT1, LAT2, 4F2hc, and ASCT2, LAT3 and ASCT1. Sections will be deparaffinized and subjected to heat-induced epitope retrieval by steaming for 15 minutes. IHC staining will be performed at the Winship Cancer Institute Research Pathology Shared Resource using an automated (DAKO) immunohistochemistry stainer and established procedures and protocols. Optimal dilutions for all antibodies will be determined empirically using archived sections from prostatectomies and blocking reagents recommended by the manufacturers. Immunohistochemical reactions will be developed with diaminobenzidine as the chromogenic peroxidase substrate. Sections will be counterstained with hematoxylin after immunohistochemistry. Specificity will be verified by negative control reactions without primary antibody. Intensity of the various immunohistochemical stains were scored blindly by a board-certified pathologist as follows; 0-

negative, 1+ (weak), 2+ (intermediate) and 3+ (strong). The expression of these markers will be correlated with FACBC uptake by ANOVA testing

C 2.3 RNA-Seq Results and Imaging Findings

RNA-Seq sequencing reads produced from the Illumina HiSeq 2000 will be mapped to the human reference genome (hg19) using Bowtie [45] and fragment reads per kilobase (FRPK) calculated using TopHat [46]. Only uniquely mapped reads will be retained for analysis. Relative changes in mRNA expression will be computed using Cufflinks and Cuffdiff [47] in a locally installed Galaxy bioinformatics environment [48, 49] deployed by the [name] laboratory.

D. Subject recruitment:

All patients will be recruited from the Emory Healthcare (Drs. [name], [name], [name] and [name]), Urology and Radiation Oncology clinics per the inclusion and exclusion criteria below.

Inclusion Criteria:

1. Patients must be 18 years of age or older.
2. Patients will have been originally diagnosed with localized (Stage T1c, T2, or T3) prostate carcinoma and have undergone what was considered definitive non-prostatectomy therapy for localized disease.

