Depending on the normality of data distribution, t-test or Wilcoxon rank sum test will be conducted to compare the mRNA differences, genomic differences in gene expression, alternative splicing, indels and single base mutations between prostate carcinoma recurrent in the prostate bed and extraprostatic samples. Analysis of variance (ANOVA) will be used to compare the IHC staining of protein levels between the different categories of FACBC uptake. Tukey pairwise comparison will be further conducted when the overall comparison with ANOVA

Version 9-23-13

Version 11-6-13

Version 11-11-14

Version 12-4-14

is significant at the significance level of 0.05. Pearson/Spearman correlation coefficients will be estimated to measure the associations: 1) between mRNA levels of candidate AAT genes and FACBC uptake; 2) between mRNA differences and quantifiable imaging biomarker data such as SUV for *anti*-[¹⁸F]FACBC PET-CT and ADC for MR. Multivariate analyses will further be conducted, in which general linear model (GLM) will be employed to assess the adjusted relationships mentioned above after adjusting for the other covariates.

Sample size and power calculation

The sample size of this study is 25 patients. The power calculation is based on the comparison of mRNA differences between the prostate bed and extraprostatic samples using two sided t-test. At the significance level of 0.05, the sample size of 25 will achieve a power of at least 80% to detect one standard deviation or higher difference in mRNA difference between the two groups of samples.

F. Adverse Event Reporting

An adverse event is defined as any untoward medical occurrence associated with the use of a drug in humans whether or not considered drug-related

A significant shift from baseline which can be attributable to the radiotracer injection and not the patient's medical condition will be considered an unexpected AE. An event greater than 7 days post scan will not be considered an AE since 95% of ligand is eliminated by 7days.

The National Cancer Institute's Common Terminology Criteria for Adverse Events (CTCAE) Version 4.03 (June 14, 2010) will be used as a guide address potential AEs subject to limitations above and medical and scientific judgment as to plausibility of such criteria in a diagnostic radiotracer study.

Adverse Event Reporting

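### Aim 2 names two unreconciled gene-level methods for expression, with no analysis of record or multiplicity rule, and its normality-switched tests suit 8-10 samples per site poorly

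*Combined protocol and SAP*

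**What the plan says.** Three parts of the combined protocol and SAP bear on how a gene is judged to differ between the two sites.

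- The statistical section for the secondary aims (E2.0) gives the tests: "Depending on the normality of data distribution, t-test or Wilcoxon rank sum test will be conducted to compare the mRNA differences". The sentence goes on to cover gene expression between bed and extraprostatic samples. It names neither the normality test nor the scale (raw or log) on which normality is judged.
- C 2.3 (RNA-Seq Results and Imaging Findings): "Relative changes in mRNA expression will be computed using Cufflinks and Cuffdiff".
- C2.0 (Study Design and Methods for Aim 2): "We will study 8-10 samples of each recurrent prostate carcinoma in the prostate bed and 8-10 samples of disease outside the prostate bed", with both sites from one patient preferred but not required. The Aim 2 text under Specific Aims adds "we believe at least 8-10 patients in whom this comparison can be directly made will be available for analysis", and the rationale describes "using the patient as his own control".

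The rationale also gives a larger expected yield of diseased sites: "approximately 23 will be expected to have disease in the prostate bed and approximately 9 will have disease in nodes".

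The only significance level in the statistics section is 0.05. No gene count, Bonferroni rule or false discovery rate is stated for this comparison. Tukey's procedure is mentioned, but only for the immunohistochemistry ANOVA.

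**The concern.** C 2.3 and E2.0 address the same contrast with different tools, do not refer to each other, and do not name one as deciding. With thousands of genes the choice of method can change which genes are reported, so it should be fixed before the reads are seen.

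The E2.0 method is also weak at this sample size, for three reasons. A normality test on 8-10 values has little information, so the test a gene receives depends partly on chance. A gene sent to the rank-sum test meets a lower limit on its p-value however large the difference. A gene sent to the t-test has its variance estimated from its own few samples alone. At stake is whether Aim 2's expression findings are reproducible and whether real differences are missed.

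**Working it through.** **The plan's own figure.** E2.0 claims at least 80% power for a 1 SD difference, two-sided 0.05, sample size 25. The noncentral t gives 93.4% for 25 v 25 unpaired, which satisfies the claim if 25 means samples per site. This is power for one test at 0.05 and does not address calling genes across a transcriptome. Whether 25 is the right count is a separate matter.

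**Inputs.** Samples per site 8-10 (C2.0), alternative yield about 23 v 9 (rationale), level 0.05 (E2.0), 7 candidate transporters (Sub-aim 2a). Assumed, because the documents give no figure: 20,000 genes tested.

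**1. Rank-sum floor.** The smallest two-sided exact p is 2/C(2n, n). One gene alone can pass Bonferroni over at most 0.05/p tests. Under Benjamini-Hochberg at 5%, genes tied at the floor pass once their number reaches 20,000 × p/0.05.

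| Samples | C(2n, n) | Smallest p | Most tests at which a lone gene passes Bonferroni | Fully separated genes needed, 5% FDR |
|---|---|---|---|---|
| 8 v 8 | 12,870 | 1.55e-4 | 321 | 62.2, so 63 |
| 9 v 9 | 48,620 | 4.11e-5 | 1,215 | 16.5, so 17 |
| 10 v 10 | 184,756 | 1.08e-5 | 4,618 | 4.3, so 5 |

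Bonferroni over 20,000 genes needs 0.05/20,000 = 2.5e-6, which none of the three sizes reaches. Over the 7 candidates it needs 0.05/7 = 0.0071, which all three reach, as they do 0.05. At 23 v 9 the floor is 2/C(32, 9) = 2/28,048,800 = 7.1e-8, below 2.5e-6.

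A paired rank test is no way out. The signed-rank floor is 2/2^n = 0.0078, 0.0039 and 0.0020 for 8, 9 and 10 pairs, all higher than the rank-sum floors.

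**2. The normality switch.** Simulating a 5% Shapiro-Wilk test in each group, with rerouting if either rejects, sends about 10% of truly normal genes to the rank-sum test at n = 8 or 10. This agrees with 1 − 0.95² = 9.8%. For log-normal values tested without a log transform, the rate is about 34-43% at log-SD 0.5 and 73-84% at log-SD 1.0. On the log scale those same genes are normal and the rate returns to about 10%.

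**3. Sharing variance.** Take a working threshold at which 5% of calls are false when 1% of genes differ and power is 50%: α × 0.99/(α × 0.99 + 0.5 × 0.01) = 0.05, so α = 0.05 × 0.005/(0.95 × 0.99) = 2.7e-4. Power for a 2 SD difference comes from the noncentral t. The noncentrality is 2√(n/2) with 2n − 2 df unpaired, or 2√n with n − 1 df paired. Variance sharing is represented by adding 4 or 10 prior df (assumed).

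| Design | Ordinary t | With 4 to 10 prior df |
|---|---|---|
| 8 v 8 unpaired | 29% | 36-43% |
| 8 pairs | 35% | 64-82% |
| 10 pairs | 67% | 86-94% |

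The paired rows take 2 SD on the paired-difference scale, so they are not comparable with the unpaired row.

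At 8 v 8 the next attainable rank-sum p is 4/12,870 = 3.1e-4, above 2.7e-4, so only complete separation counts. For a 2 SD normal difference that happens in about 16% of simulated samples, against 29% for the t-test. Being rerouted therefore has a real cost.

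**The case against.** **The methods may not conflict.** C 2.3 is a bioinformatics section and says that changes are computed, without mentioning significance. A fair reading is that Cufflinks and Cuffdiff quantify and E2.0 tests. This stands: a reader might infer a contradiction, but the documents show only that the roles are not reconciled and no analysis of record is named.

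**The floor may not bind.** A reader might infer that the rank-sum test can never call a gene at these sizes. The documents do not support that. They state 0.05 and no genome-wide correction. At 0.05 or over the 7 candidates the test can call a gene. All three floors lie below the 2.7e-4 threshold used above. At the rationale's yield of about 23 v 9 the floor is negligible. What stands is the conditional statement: the floor blocks every gene at 8-10 per site under genome-wide Bonferroni, and it can block calls under a false discovery rate when few genes separate completely.

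**The large rerouting rates rest on a choice the plan does not make.** They require skewed data tested unlogged. Only the figure of about 10% holds without that.

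**The gains are assumed.** The prior df are not from the documents, and the 8-pair contrast is the most favourable case shown; at 10 pairs an ordinary t already reaches 67%. This stands as a limit on size. In each design shown the direction is the same.

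**Aim 2 is secondary, in a preliminary trial, with RT-PCR confirmation planned.** This limits the severity. Confirmation applies only to changes the RNA-seq analysis has identified, so it cannot recover genes that were missed.

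**Conclusion.** The concern holds in a bounded form. E2.0 and C 2.3 leave open which result decides that a gene differs, and no error rate across genes is set. That much follows from the text alone. At 8-10 samples per site the normality switch reroutes about 10% of normal genes by chance, and the unshared variance costs power: 29% against 36-43% at 8 v 8 unpaired, given a 2 SD difference, a 2.7e-4 threshold and 4-10 prior df.

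The rank-sum floor is a consequence to guard against. It is decisive only with about 8-10 samples per site and Bonferroni correction over more tests than the limits shown (321 to 4,618), for example the assumed 20,000 genes. Aim 1 is unaffected. The plan should be changed before sequencing data are analysed, but the point concerns a secondary aim.

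**What to change.** In E2.0, for expression only:

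- Replace the normality-switched t-test or rank-sum test with one count-based model that shares variance across genes (limma-voom, edgeR or DESeq2), run from raw gene counts, and name it as the analysis of record.
- State a 5% false discovery rate for the bed versus extraprostatic comparison, and the set of genes over which it applies.
- In C 2.3, describe Cuffdiff output as a secondary display, with a cross-reference to E2.0.

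The cost is SAP wording and free software on the same reads, with no extra tissue or sequencing. The downside is that the deciding analysis leaves the Cuffdiff pipeline already installed, so a raw-count step has to be set up.
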